8.6 Assessing and Recording Adverse Events

An adverse event is defined as any untoward medical occurrence in a patient or clinical investigation subject administered a pharmaceutical product and which does not necessarily have to have a causal relationship with this treatment. An adverse event can therefore be any unfavorable and unintended sign (including an abnormal laboratory finding, for example), symptom, or disease temporally associated with the use of a medicinal product or protocol-specified procedure, regardless of whether the event is considered related to the medicinal product or protocol-specified procedure. Any worsening (i.e., any clinically significant adverse change in frequency and/or intensity) of a preexisting condition that is temporally associated with receipt of study therapy, is also an adverse event.

Adverse events may occur during study therapy or within the follow-up period specified by the protocol, from overdose (whether accidental or intentional), from abuse and from withdrawal.

Only adverse events that meet the following definition will be recorded:

1. All grade 3 and higher adverse events
2. Grade 1-2 adverse events that require medical intervention, i.e. initiation of a new medication, or are otherwise clinically significant at the discretion of the investigator
3. Any adverse event that requires a dose reduction or dose delay of either bomedemstat or atezolizumab

Adverse events will be recorded from Cycle 1 Day 1 until the Safety Monitoring visit performed according to the Study Calendar (Section 7.0), using the Adverse Event case report forms/worksheets. For subjects who discontinue study therapy for a reason other than disease progression and are being followed with Monitoring visits (Section 8.5.3.3), adverse events should continue to be monitored. Adverse events related to either bomepedemstat or atezolizumab will be followed until resolution or stabilization of the AE or until the beginning of a new anti-neoplastic therapy, whichever occurs first. The reporting timeframe for adverse events meeting any serious criteria is described below.

8.6.1 Serious Adverse Events

SAEs will be reported promptly, using the SAE Report Form, once the Investigator determines that the event meets the protocol definition of an SAE. The Investigator or designee will report the SAE within 24 hours of his/her becoming aware of these events regardless of relationship of the SAE to the use of study drug, in accordance with the instructions in the SAE Report Form Completion Guidelines. The Investigator will always provide an assessment of relatedness at the time of the initial report. The SAE Report will always be completed as thoroughly as possible with all available details of the event within the designated time frames. Copies of relevant patient records, autopsy reports, and other documents may be requested.

A detailed SAE reporting procedure and contact information will be included in the SAE Report Form Completion Guidelines which will be finalized before any patients are consented. If the Investigator does not have all information regarding an SAE, he/she will not wait to receive additional information before reporting the SAE. The SAE Report will be updated when additional information is received within 24 hours of receipt of such information.

The Institutional Review Board (IRB) must be notified in writing of any SAEs that require expedited reporting to Regulatory Authorities. All SAEs meeting expedited reporting requirements will be reported to FDA in accordance with reporting requirements.

A Serious Adverse Event (SAE), which must be reported to the Principal Investigator within 24 hours of awareness via pager, is any adverse event that meets any of the following criteria:

1. Fatal (i.e., the adverse event directly causes or leads to death)
2. Life-threatening (i.e., the adverse event, in the view of the Investigator, places the subject at immediate risk of death). Note: this does not include any adverse event that, had it occurred in a more severe form or was allowed to continue, might have caused death
3. Requires or prolongs inpatient hospitalization
4. Results in persistent or significant disability/incapacity (i.e., the adverse event results in substantial disruption of the subject's ability to conduct normal life functions)
5. Congenital anomaly/birth defect in a neonate/infant born to a mother exposed to study drug
6. Significant medical event in the Investigator's judgment (e.g., may jeopardize the subject or may require medical/surgical intervention to prevent one of the outcomes listed above)
7. Encephalopathy of any grade (see Section 10.2.1)

Death that is clearly the result of disease progression should be documented but should not be reported as an SAE.

8.6.2 Overdose

An overdose for bomedemstat will be defined as any dose of study drug(s) that is 10% or more over the prescribed dose per cycle as described in the study protocol. The investigator must notify the Principal Investigator of this event via pager within 24 hours of awareness (although not considered an SAE).

No specific information is available on the treatment of overdose of bomedemstat. There is no specific antidote for bomedemstat overdose. In clinical studies, the highest total daily dose tested was 6 mg/kg/d. Aside from expected hematologic toxicities, no recurrent adverse events were noted up to the 6 mg/kg/d dose. The pharmacological effects may be prolonged after serum levels of active bomedemstat are no longer present. It is not known if bomedemstat is dialyzable. In the event of overdose, bomedemstat should be held and the patient should be observed closely for signs of toxicity. Appropriate supportive treatment should be provided as clinically indicated.

8.6.3 Pregnancy

8.6.3.1 Maternal exposure

If a patient becomes pregnant during study participation, bomedemstat will be discontinued immediately and permanently and the subject will be ineligible for further receipt of treatment in the study.

Pregnancy itself is not regarded as an AE unless there is a suspicion that bomedemstat and/or atezolizumab may have interfered with the effectiveness of a contraceptive medication. Congenital abnormalities or birth defects and spontaneous miscarriages should be reported and handled as SAEs. Elective abortions without complications should not be handled as AEs. The outcome of all pregnancies (spontaneous miscarriage, elective termination, ectopic pregnancy, normal birth, or congenital abnormality) should be followed up and documented even if the patient was discontinued from the study.

If any pregnancy occurs in the course of the study, then the Investigator or other site personnel should inform the Principal Investigator within 1 day, *i.e.* immediately, but no later than 24 hours of when he or she becomes aware of it.

The designated study representative will work with the Investigator to ensure that all relevant information is provided to the sponsor approved Patient Safety data entry site within 1 to 5 calendar days for SAEs and within 30 days for all other pregnancies.

The same timelines apply when outcome information is available.

8.6.3.2 Paternal exposure

Male patients should refrain from fathering a child or donating sperm during the study and for 30 days after the last dose of bomedemstat and 90 days after the last dose of atezolizumab, whichever is longer.

Pregnancy of the patient's partner is not considered to be an AE. However, the outcome of all pregnancies (spontaneous miscarriage, elective termination, ectopic pregnancy, normal birth, or congenital abnormality) occurring from the date of the first dose until 90 days after the last dose of study treatment, if possible, be followed up and documented.

Where a report of pregnancy is received, prior to obtaining information about the pregnancy, the Investigator must obtain the consent of the patient's partner. Therefore, the local study team should adopt the generic ICF template in line with local procedures and submit it to the relevant Ethics Committees (ECs)/Institutional Review Boards (IRBs) prior to use.

9.0 CRITERIA FOR EVALUATION AND ENDPOINT ANALYSIS

9.1 Measurability of Lesions

9.1.1 *Measurable disease*

Note that measurable disease is defined differently for malignant lymph nodes vs other disease as follows.

Lesions other than malignant lymph nodes that can be accurately measured in at least one dimension (longest diameter to be recorded) as ≥ 2.0 cm by chest x-ray, by ≥ 1.0 cm with CT or MRI scans, or ≥ 1.0 cm with calipers by clinical exam. All tumor measurements must be recorded in decimal fractions of centimeters (or millimeters).

The defined measurability of lesions on CT scan is based on the assumption that CT slice thickness is 0.5 cm or less. It is strongly recommended that CT slice of 0.5 cm be used. If CT scans have slice thickness greater than 0.5 cm, the minimum size for a measurable lesion should be twice the slice thickness.

Malignant lymph nodes are to be considered pathologically enlarged and measurable if it measures ≥ 1.5 cm in short axis (greatest diameter perpendicular to the long axis of the lymph node) when assessed by scan (CT scan slice recommended being no greater than 0.5 cm).

9.1.2 *Non-measurable disease*

All other lesions (or sites of disease), including small lesions (longest diameter < 1.0 cm or pathologic lymph nodes with ≥ 1.0 cm to <1.5 cm short axis), are considered non-measurable disease. Bone lesions, leptomeningeal disease, ascites, pleural/pericardial effusions, lymphangitis cutis/pneumonitis, inflammatory breast disease, and abdominal masses (not followed by CT or MRI), are considered as non-measurable as are previously radiated lesions that have not progressed.

9.1.3 *Notes on measurability*

1. For CT and MRIs, the same type of scanner should be used and the image acquisition protocol should be followed as closely as possible to prior scans. It is no longer necessary to distinguish between spiral and conventional CT.
2. Body scans should be performed with breath-hold scanning techniques, if possible.
3. PET-CT: At present, the low dose or attenuation correction CT portion of a PET-CT is not always of optimal diagnostic CT quality for use with RECIST measurements. However, if the site can document that the CT performed as part of a PET-CT is of identical diagnostic quality to a diagnostic CT, then the CT portion of the PET-CT can be used for RECIST measurements and can be used interchangeably with stand-alone CT. The slice thickness of 0.5 cm or less is highly recommended. If CT scans have slice thickness > 0.5 cm, the minimum size for a measurable lesion should be twice the slice thickness.
4. Ultrasound: Ultrasound is not useful in assessment of lesion size and should not be used as a method of measurement.
5. Cystic lesions that meet the criteria for radiographically defined simple cysts should not be considered as malignant lesions (neither measurable nor non-measurable) since they are, by definition, simple cysts.
6. If a target lesion becomes very small some radiologists indicate that it is too small to measure. If the lesion is still present, a default measurement of 0.5 cm should be applied.

7. If the radiologist believes the lesion is no longer discernible, a default measurement of 0.0 cm should be recorded.

9.2 Objective Status at Radiographic Evaluation

Objective Status is to be recorded at each evaluation. All measurable lesions up to a maximum of 2 lesions per organ, 5 lesions in total, representative of all involved organs, should be identified as target lesions at baseline. All other lesions (or sites of disease) including any measurable lesions over and above the 5 target lesions should be identified as non-target lesions. Measurements must be provided for target measurable lesions, while presence or absence must be noted for non-target measurable and non-measurable disease.

For studies that use disease progression as an endpoint, all potential sites of metastases should be evaluated at each time point rather than following only sites of disease identified at baseline. It is acceptable to image only the areas of the body most likely to be involved with metastatic disease for the tumor type (chest, abdomen, pelvis, and/or bone scan are typical), with the addition of any areas with suspected involvement based upon clinical symptoms. For study-specific imaging requirements, see the Study Calendar in Section 7.0.

9.2.1 Complete Response (CR)

Complete disappearance of all target and non-target lesions (with the exception of lymph nodes mentioned below). No new lesions. No disease related symptoms. Any lymph nodes (whether target or non-target) must have reduction in short axis to < 1.0 cm. All disease must be assessed using the same technique as baseline.

9.2.2 Partial Response (PR)

Applies only to participants with at least one measurable lesion. Greater than or equal to 30% decrease under baseline of the sum of appropriate diameters of all target measurable lesions. No unequivocal progression of non-measurable disease. No new lesions. All target measurable lesions must be assessed using the same techniques as baseline.

9.2.3 Stable Disease

Does not qualify for CR, PR, PD or Symptomatic Deterioration. All target measurable lesions must be assessed using the same techniques as baseline.

9.2.4 Progressive Disease / Disease Progression (PD)

One or more of the following must occur:

1. 20% increase in the sum of appropriate diameters of target measurable lesions over smallest sum observed (over baseline if no decrease during therapy) using the same techniques as baseline, as well as an absolute increase of at least 0.5 cm.
2. Unequivocal progression of non-measurable disease in the opinion of the treating physician (an explanation must be provided).
3. Appearance of any new lesion/site (see Section 9.2.4.2 for details).
4. Death due to disease without prior documentation of progression and without symptomatic deterioration.

9.2.4.1 Confirmation of PD

Unconfirmed disease progression is defined as a single disease assessment showing disease progression as defined above. Confirmed disease progression is defined as a second determination of progression at least 4 weeks after the initial report of progression.

If the second assessment documents an absence of progression, the participant's disease is deemed not to have progressed and the initial report of progression is coded as a pseudo-progression. If there are no additional disease assessments at least 4 weeks after the initial assessment documenting absence of progression (either due to inadequate or missing assessment) then the initial assessment will be coded as a progression. Any indication of progression (per the definition above) reported after the determination of pseudo-progression will be coded a progression and will not require a second assessment to confirm progression.

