5.2 Exclusion Criteria

Subjects meeting any of the following exclusion criteria are not eligible for study participation:

1. Prior receipt of systemic therapy for ES-SCLC other than four cycles of induction platinum- etoposide and immune checkpoint inhibitor (see Section 5.1 for definitions of these terms).
2. Diagnosis of LS-SCLC that has not been previously treated.
3. Receipt of radiation therapy for symptomatic deterioration and/or radiographic disease progression that was administered after initiation of induction platinum- etoposide and immune checkpoint inhibitor.

Note: the presence of untreated asymptomatic brain metastasis, or a history of receipt of radiation to brain metastasis that was not initiated in response to symptomatic deterioration and/or radiographic disease progression following initiation of induction systemic therapy, does not preclude study participation. Investigators should contact the PI if clarification is needed.

4. Anticipated use of prophylactic cranial irradiation or consolidative thoracic radiation therapy during study participation.

Note: Palliative radiation to the CNS for new CNS disease that develops during study participation is allowed (Section 8.2.7.1).

5. History of prior immune-related adverse event or other toxicity associated with immune checkpoint inhibitor that precludes safe administration of maintenance atezolizumab, in the opinion of the investigator.

6. Current or prior use of immunosuppressive medication within 14 days prior to the first dose of study treatment. The following are exceptions to this criterion:
 - a. Intranasal, inhaled, topical steroids or local steroid injections (e.g., intra-articular injection).
 - b. Systemic corticosteroids at doses not to exceed 10 mg/d of prednisone or equivalent.
 - c. Steroids as premedication for hypersensitivity reactions (e.g., CT scan premedication).
7. Active autoimmune disease requiring systemic immunosuppression or history of autoimmune disease requiring systemic immunosuppression within the last 2 years.

Note: Systemic immunosuppression should be interpreted as systemic glucocorticoids at a dose of greater than 10 mg/day of prednisone or equivalent, systemic biologic agents including monoclonal antibodies against inflammatory mediators, or small molecule agents. Investigators should contact the PI if clarification is needed.

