8.2.7.1 Isolated Central Nervous System Progression

Isolated CNS progression does not require discontinuation of study treatment. Bomedemstat should be held for seven days prior to until seven days following the administration of CNS-directed therapy (e.g. a standard course of whole brain radiotherapy or stereotactic radiosurgery, in accordance with institutional practice). The subject may then resume study therapy when clinically appropriate. If more than 4 weeks have elapsed since the previous dose of study drug, the subject should undergo a radiographic disease assessment before restarting study treatment.

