9.6 Progression-Free Survival (PFS)

From the date of registration to the date of first document of PD or symptomatic deterioration (as defined above), or death due to any cause. PFS for participants last known to be alive without report of progression, symptomatic deterioration, or death is censored at date of last contact.

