10.3 Sample Size Justification and Analysis Plans

The total accrual goal to this study is 34 eligible patients. Based on the IMPOWER133 study, we estimate that 35% of patients with ES-SCLC are alive and free from disease progression at 6 months after initiation of maintenance anti-PD(L)1 therapy. With 34 patients, this study design has 90% power to detect a 25% improvement in 6-month PFS rates (from 35 to 60%) using a 1-sided binomial test at the 5% level. The observation of 17 patients progression-free (i.e. alive without PD or symptomatic deterioration) at 6 months (a 50% rate) would be considered evidence to rule out a 35% 6-month PFS rate. With 34 patients, proportions can be estimated to within 17% with 95% confidence and any toxicity with at least 10% prevalence is likely to be observed with 97% confidence.

Additional analyses will evaluate proportions (such as toxicity or response rates within subgroups) accompanied by 95% confidence intervals. Distributions for time-to-event outcomes (PFS, OS) will be evaluated using the method of Kaplan-Meier. For point estimates at landmark times, the associated 95%

confidence interval (CI) will be calculated using Greenwood's formula and based on a log-log transformation applied on the survival function.

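### The pseudo-progression rule has no exception for a lesion given local therapy, so an irradiated CNS progression could be counted as a 6-month PFS success

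*Combined protocol and SAP*

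**What the plan says.** **Definition and confirmation of PD.** Section 9.2.4 counts any new lesion as PD. Section 9.2.4.1 asks for a second determination at least 4 weeks after the first. If the second assessment does not show progression, the patient is treated as not having progressed and "the initial report of progression is coded as a pseudo-progression". If the second assessment is missing or inadequate, the first PD stands. Any progression reported after a pseudo-progression counts without confirmation. Section 9.2.4.2 adds that a new lesion confirmed on repeat scans is dated to the initial scan.

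**Isolated CNS progression.** Section 8.2.7.1 says "Isolated CNS progression does not require discontinuation of study treatment" and describes CNS-directed therapy followed by resumption of study treatment. Section 6.1 calls the event disease progression and lets the patient continue after definitive CNS therapy. Section 6.4.3 exempts radiation for isolated CNS progression from the ban on radiotherapy.

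**PFS.** Section 9.6 runs PFS from registration to "the date of first document of PD or symptomatic deterioration (as defined above"), or to death. It censors living patients for whom no progression or symptomatic deterioration has been reported.

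**Primary analysis.** Section 10.3 sets the size: "The total accrual goal to this study is 34 eligible patients". It tests the 6-month PFS rate ("from 35 to 60%) using a 1-sided binomial test at the 5% level") and takes 17 patients progression-free at 6 months as ruling out 35%.

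**The concern.** The recode is meant for apparent progression that turns out not to be real. As worded, it looks only at what the second assessment shows, not at why the finding went away. If a brain lesion has been irradiated in between, its absence on the next scan reflects the local therapy. It says nothing about whether the initial scan showed true progression, and nothing about study drug. No section says whether such a patient remains a PFS event.

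The situation is plausible in this population. Section 5.2 excludes "Anticipated use of prophylactic cranial irradiation or consolidative thoracic radiation therapy during study participation", and its note on radiation accepts untreated asymptomatic brain metastases at entry. The primary endpoint is a count of 34 patients against a fixed cut-off, so the classification of one or two patients can decide the result. If the rule is left open, it will be settled by adjudication after the outcomes are known.

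**Working it through.** **1. Inputs (section 10.3).** n = 34; null rate 35% ("we estimate that 35% of patients with ES-SCLC are alive and free from disease progression at 6 months"); alternative 60%; success if at least 17 of 34 are progression-free at 6 months. The number of patients recoded after local therapy is not given in the documents. One or two is an assumed range.

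**2. The plan's own figure.** The plan states that "this study design has 90% power to detect a 25% improvement in 6-month PFS rates". With X the number of successes, exact binomial:

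- Power = P(X ≥ 17 | n = 34, p = 0.60) = 0.913, consistent with the stated 90%.
- Type I error = P(X ≥ 17 | n = 34, p = 0.35) = 0.051, which rounds to the stated 5%.

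The design reproduces.

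**3. Effect of recoding k true progressions.** Each recoded patient adds 1/34 = 2.9 percentage points to the observed rate, provided the patient has no other event before 6 months. There are two simple ways to express this at a true 35% rate:

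- *Shifted cut-off:* exactly k failures are counted as successes, so 17 − k true successes suffice. The false-positive rate is P(X ≥ 17 − k | 0.35).
- *Shifted rate:* k are recoded on average, so the apparent rate is 0.35 + k/34. The false-positive rate is P(X ≥ 17 | 0.35 + k/34).

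| k (assumed) | Shifted cut-off | Apparent rate | Shifted rate |
|---|---|---|---|
| 0 | 0.051 | 0.350 | 0.051 |
| 1 | 0.099 | 0.379 | 0.103 |
| 2 | 0.174 | 0.409 | 0.182 |

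The two agree closely. One recoded patient roughly doubles the false-positive rate, and two take it to 17-18%.

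**4. Which patients could be recoded.** Taking the sections together:

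- *New CNS lesion, smaller but still visible after therapy:* under 9.2.4.2 the repeat scan confirms a new lesion, so PD stands from the initial scan.
- *New CNS lesion that has vanished:* absence of progression under 9.2.4.1, so the recode is open.
- *Known CNS disease that progressed and, after therapy, no longer meets PD criteria:* the recode is open.
- *No adequate second assessment:* PD stands under 9.2.4.1.
- *Later PD, symptomatic deterioration or death before 6 months:* the patient is an event anyway.

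**5. Does 9.6 resolve the open cases?** Its reference back to the PD definition can be read as importing 9.2.4.1, which makes the patient a non-event. Its censoring clause, however, covers only patients with no report of progression, and 9.2.4.1 itself describes the reversed finding as an initial report of progression. A living, recoded patient fits neither clause cleanly.

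**The case against.** The strongest reply is that the CNS pathway is separate. Sections 6.1 and 8.2.7.1 call these events progression and handle them apart from the unconfirmed-PD pathway in 8.2.7.2. No sentence applies pseudo-progression coding to an irradiated CNS lesion. That is a reasonable reading of intent, but 9.2.4.1 is written for any PD and carries no exclusion, so the text permits the recode.

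The limits listed in step 4 also stand, and they narrow the problem. CNS imaging narrows it further. Sections 7.0 and 8.2.7 address it only for patients with known CNS disease at enrolment, by usual practice, and a body CT alone can hardly show that a brain lesion has gone. Section 9.2.7, however, defines an inadequate assessment through target lesions and methods, so it does not expressly require repeat CNS imaging.

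A reader might infer more than the documents support:

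- *That 9.6 contradicts 9.2.4.1.* It does not. Section 9.6 refers back to PD as already defined, and 9.2.4.1 sits within that definition. The wording is unreconciled rather than contradictory.
- *That any shrinkage after radiotherapy erases the event.* For new lesions, 9.2.4.2 prevents this while the lesion remains visible.
- *That starting other anticancer therapy opens the same route.* This is largely closed. Sections 6.1, 8.5.3.3 and 8.5.3.4 move such patients to survival follow-up, and without a second assessment the first PD stands.

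**Conclusion.** The point holds as a gap in the endpoint definition. Section 9.2.4.1, applied as written, can turn a true CNS progression cleared by local therapy into a 6-month success, and 9.6 does not settle the classification. It should be corrected before the primary analysis.

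The false-positive figures of about 10% and 17-18%, against 5.1%, rest on an assumed one or two recoded patients who have no other event before 6 months. The documents give no frequency of isolated CNS progression, so the likely number cannot be derived. The figures show how sensitive the 17-of-34 rule is. They do not predict the error rate.

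A reader might also infer that the 6-month count is biased in favour of bomedemstat. That is not shown. Relative to counting every first PD, the recode can only raise the count, but reversing a genuine pseudo-progression is not bias. Section 10.3 does not say how progression was counted in the source of the 35% benchmark, so the direction against that benchmark is unknown. Nor do the documents support dropping pseudo-progression coding altogether. For lesions without local therapy it is a defensible endpoint choice.

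**What to change.** 1. In 9.2.4.1 and 9.6, state that, for the PFS endpoint, PD followed by local therapy to the progressing site before the second assessment (including CNS-directed therapy under 8.2.7.1) cannot be coded as pseudo-progression and is an event on the date first documented.
2. Reword the censoring clause in 9.6 so that a patient validly coded as pseudo-progression under 9.2.4.1 clearly falls under one clause.
3. Add to 10.3 a sensitivity analysis of the 6-month rate that counts every first documented PD as an event.
4. Keep pseudo-progression coding for lesions that received no local therapy, and leave the treatment-continuation rules as they are.

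The cost is a few sentences and one extra tabulation, with no added scans or patients. The sample size, the cut-off of 17 and the power of 0.913 are unchanged. The downside is that the 6-month rate may look slightly less favourable.
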